8.1.6. Retained Samples for Biomarker Testing

For all subjects, sera will be collected at Day 4 and Day 60 (as applicable) and stored for potential biomarker assessment at a central laboratory and comparison to testing of an aliquot of sera obtained at Day 1 and Day 57, respectively

Additionally, in the event that a subject develops symptoms compatible with myocarditis and/or pericarditis or the site is notified of a diagnosis of myocarditis and/or pericarditis, occurring within 4 weeks from vaccination, the site will follow with an in-person unscheduled illness and collect serum for potential biomarker testing at a central laboratory.

The following sample will be collected:

- 4 mL SST collection for potential biomarker testing at a central laboratory

8.2 Safety and Other Assessments

All safety endpoints for this trial are obtained by reporting of adverse events.

- New symptoms will be queried with both broad open-ended questions at the Day 8 telephone call and by specifically asking about symptoms of chest pain, shortness of breath or palpitations that may represent myocarditis and/or pericarditis.
- Data on new medical conditions, doctors' office visits (outside of routine care), emergency room visits, and hospitalizations will be collected.
- Memory Aid: All subjects will complete a Memory Aid from the time of each vaccination through 7 days after each vaccination. Subjects will be asked to confirm completion of the Memory Aid and will be queried on the presence of any grade 3 symptoms. Based on the information provided, subjects may be asked to return to the clinic for evaluation. Fourteen days after each vaccination, Memory Aids are reviewed thoroughly with the subject and confirmed data recorded in the CRF.

As these are similar to licensed vaccines, there are no laboratory assessments for safety that will be done for this trial.

8.3 Adverse Events and Serious Adverse Events

8.3.1 Definition of Adverse Event (AE)

AE means any untoward medical occurrence associated with the use of an intervention in humans, whether or not considered intervention-related [21 CFR 312.32 (a)]. An AE can therefore be any unfavorable and unintended sign, symptom or disease temporally associated with the use of medicinal (investigational) product.

Any medical condition that is present at the time that the subject is screened will be considered as baseline and not reported as an AE. However, if the severity of any pre-existing medical condition increases, it should be recorded as an AE.

AEs can be further divided into solicited AEs and unsolicited AEs. Solicited AEs are those that are described in the package insert as local or systemic reactogenicity occurring in the first 7 days after vaccination. Unsolicited AEs are those events that the subject reports occurring without being queried about the specific event.

AEs will be assessed for severity and relationship to study intervention ([Section 8.3.4](#)). Reporting of all AEs, solicited and unsolicited, will occur during the period from study product administration on Day 1 through 28 days after each vaccination. After 28 days post last vaccination through the end of study, only SAEs, Protocol Specified AESIs, MAAEs, NOCMCs, and AEs leading to withdrawal from the study will be reported.

All AEs, solicited and unsolicited, will be captured on the appropriate DCF. Solicited AEs will be regarded as related to the study product and will not require separate entry into the AE log. Information to be collected for unsolicited AEs includes event description, date of onset, assessment of severity, relationship to study product and alternate etiology (assessed only by those with the training and authority to make a diagnosis and listed on the Form FDA 1572 as the participating site PI or appropriate sub-investigator), date of resolution, seriousness, and outcome. AEs occurring during the study-collection and reporting period will be documented appropriately regardless of relationship.

AEs will be followed to resolution or stabilization.

8.3.1.1 Solicited Adverse Events

Solicited AEs are anticipated local and systemic AEs for which consistent collection of information is desired. Study clinicians will follow and collect resolution information for any reactogenicity symptoms that are not resolved within 7 days.

Solicited AEs (i.e., reactogenicity) will be collected using a memory aid and confirmed data recorded on the appropriate DCF from the time of each vaccination through 7 days post each vaccination.

For this study, solicited AEs will be:

- Injection site Pain
- Injection site Erythema
- Injection site Edema/Induration
- Headache
- Fatigue
- Myalgia
- Arthralgia
- Nausea
- Fever
- Chills

8.3.1.2 Unsolicited Adverse Events

All AEs spontaneously reported by the subject and/or in response to an open question from study staff or revealed by observation, physical examination or other diagnostic procedures must be recorded on the appropriate DCF.

Unsolicited AEs of all severities will be reported from the time of study product administration through 28 days post each vaccination.

After 28 days post last vaccination through the end of study, only SAEs, AESIs, NOCMCs, MAAEs, and AEs leading to withdrawal from the study (as detailed in [Section 8.3.7](#) and [8.3.9](#)) will be reported.

8.3.2 Definition of Serious Adverse Event (SAE)

An SAE is defined in 21 CFR 312.32 as follows: “An AE or suspected adverse reaction is considered serious if, in the view of either the participating site PI or appropriate sub-investigator or the sponsor, it results in any of the following outcomes:

- Death,
- a life-threatening AE,
- inpatient hospitalization or prolongation of existing hospitalization,
- a persistent or significant incapacity or substantial disruption of the ability to conduct normal life functions,
- or a congenital anomaly/birth defect.

Important medical events that may not result in death, be life-threatening, or require hospitalization may be considered serious when, based upon appropriate medical judgment, they may jeopardize the patient or subject and may require medical or surgical intervention to prevent one of the outcomes listed in this definition. Examples of such medical events include allergic bronchospasm requiring intensive treatment in an emergency room or at home, blood dyscrasias or convulsions that do not result in inpatient hospitalization, or the development of drug dependency or drug abuse.”

“Life-threatening” refers to an AE that at occurrence represents an immediate risk of death to a subject. An event that may cause death if it occurs in a more severe form is not considered life-threatening. Similarly, a hospital admission for an elective procedure is not considered an SAE.

All SAEs, as with any AE, will be assessed for severity and relationship to study intervention.

All SAEs will be recorded on the appropriate SAE DCF.

All SAEs will be followed through resolution or stabilization by a study clinician, licensed to make medical diagnoses and listed on the Form FDA 1572 as the participating site PI or appropriate sub-investigator.

All SAEs will be reviewed and evaluated by DMID and will be sent to the DSMB (for periodic review unless related) and IRB/IEC as needed.

8.3.3 Suspected Unexpected Serious Adverse Reactions (SUSAR)

A SUSAR is any SAE where a causal relationship with the study product is at least reasonably possible but is not listed in the Investigator's Brochure (IB), Package Insert, and/or Summary of Product Characteristics.

8.3.4 Classification of an Adverse Event

The determination of seriousness, severity and causality will be made by an on-site investigator who is qualified (licensed) to diagnose AE information, provide a medical evaluation of AEs and classify AEs based upon medical judgment. This includes, but is not limited to, physicians, physician assistants and nurse practitioners.

8.3.4.1 Severity of Adverse Events

All AEs, AESIs, NOCMCs, MAAEs, SAEs, and AEs leading to withdrawal from the study will be assessed for severity, according to the toxicity grading scales in the FDA "Toxicity Grading Scale for Healthy Adult and Adolescent Volunteers Enrolled in Preventive Vaccine Clinical Trials".

For AEs not included in the FDA-defined grading system, the following guidelines will be used to describe severity.

Mild (Grade 1): Events that are usually transient and may require only minimal or no treatment or therapeutic intervention and generally do not interfere with the subject's usual activities of daily living.

Moderate (Grade 2): Events that are usually alleviated with additional specific therapeutic intervention. The event interferes with usual activities of daily living, causing discomfort but poses no significant or permanent risk of harm to the research subject.

Severe (Grade 3): Events interrupt usual activities of daily living, or significantly affect clinical status, or may require intensive therapeutic intervention. Severe events are usually incapacitating.

AEs characterized as intermittent require documentation of onset and duration of each episode. The start and stop date of each reported AE will be recorded on the appropriate DCF. Changes in the severity of an AE will be documented to allow an assessment of the duration of the event at each level of intensity.

8.3.4.2 Relationship to Study Intervention

For each reported adverse reaction, the participating site PI or qualified designee must assess the relationship of the event to the study product using the following guidelines:

- Related – The AE is known to occur with the study intervention, there is a reasonable possibility that the study intervention caused the AE, or there is a temporal relationship between the study intervention and event. Reasonable possibility means that there is evidence to suggest a causal relationship between the study intervention and the AE.
- Not Related – There is not a reasonable possibility that the administration of the study intervention caused the event, there is no temporal relationship between the study intervention and event onset, or an alternate etiology has been established.

Solicited adverse events reported in the 7 days after each vaccination are considered related to study product unless they are also recorded as an unsolicited event, in which case the relationship to study product will be determined by the PI or qualified designee.

8.3.5 Time Period and Frequency for Event Assessment and Follow-Up

For this study:

- Solicited Adverse Events will be collected for 7 days following each vaccine dose.
- Unsolicited AEs will be collected until 28 days after each vaccination.
- AESIs, NOCMCs, MAAEs, SAEs, and AEs leading to withdrawal from the study will be collected from Day 1 through the end of the study.

8.3.6 Adverse Event Reporting

8.3.6.1 Investigators Reporting of AEs

Information on reportable AEs should be recorded on the appropriate DCF. All clearly related signs, symptoms and results of diagnostic procedures performed because of an AE should be grouped together and recorded as a single diagnosis. If the AE is a clinical laboratory abnormality that is part of a clinical condition or syndrome, it should be recorded as the syndrome or diagnosis rather than the individual clinical laboratory abnormality. Each AE will also be described in terms of duration (start and stop date), severity, association with the study product, action(s) taken, and outcome.

8.3.7 Serious Adverse Event Reporting

8.3.7.1 Investigators Reporting of SAEs

Any AE that meets a protocol-defined criterion as an SAE must be submitted immediately (within 24 hours of site awareness) on an SAE form to the DMID Pharmacovigilance Group, at the following address:

DMID Pharmacovigilance Group
Clinical Research Operations and Management Support (CROMS)
[name]
[name]
SAE Hot Line: [name] (US) or [name] (outside US)
SAE [contact] (US) or [name] (outside US)
SAE Email Address: [contact]

In addition to the SAE form, select SAE data fields must also be entered into Advantage eClinical. Refer to the protocol-specific MOP for details regarding this procedure.

Other supporting documentation of the event may be requested by the DMID Pharmacovigilance Group and should be provided as soon as possible. The DMID Medical Monitor will review and assess the SAE for regulatory reporting and potential impact on study subject safety and protocol conduct.

At any time after completion of the study, if the participating site PI or appropriate sub-investigator becomes aware of an SAE that is suspected to be related to study product, the participating site PI or appropriate sub-investigator will report the event to the DMID Pharmacovigilance Group.

8.3.7.2 Regulatory Reporting of SAEs

Following notification from the participating site PI or appropriate sub-investigator, DMID, as the IND sponsor, will report any SUSAR in an IND safety report to the FDA and will notify all participating site PIs (i.e., all PIs to whom the sponsor is providing drug under its IND(s) or under any PI's IND(s)) of potential serious risks from clinical studies or any other source, as soon as possible. DMID will report to the FDA any unexpected fatal or life-threatening suspected adverse reaction as soon as possible, but in no case later than 7 calendar days after the sponsor's initial receipt of the information. If the event is not fatal or life-threatening, the IND safety report will be submitted within 15 calendar days after the sponsor determines that the information qualifies for reporting as specified in 21 CFR Part 312.32. Relevant follow-up information to an IND safety report will be submitted as soon as the information is available. Upon request from FDA, DMID will submit to the FDA any additional data or information that the agency deems necessary, as soon as possible, but in no case later than 15 calendar days after receiving the request.

SAEs that are not SUSARs will be reported to the FDA at least annually in a summary format which includes all SAEs.

8.3.8 Reporting Events to Subjects

Subjects will be informed of any major safety event that occurs as part of their participation in this trial.

8.3.9 Adverse Events of Special Interest (AESIs), New Onset of Chronic Medical Conditions (NOCMCs) and Medically Attended Adverse Events (MAAEs)

Adverse Events of Special Interest (AESIs) represent any events for which additional data (besides the standard AE data) are desired. An adverse event of special interest (serious or nonserious) is one of scientific and medical concern specific to the sponsor's product or program, for which ongoing monitoring and rapid communication by the investigator to the sponsor is required. Such an event may require further investigation in order to characterize and understand it. Depending on the nature of the event, rapid communication by the trial sponsor to other parties (e.g., regulators) may also be required. These may be at the request of the regulatory agency, industry partner or DMID, and driven by a regulatory requirement, or known or potential risk from the product or class.

Protocol Specified AESIs are listed in [Section 12](#). In addition, for stage 3, AESIs will also include a list of pIMD.

Potential Immune-mediated Diseases (pIMDs)

Potential immune-mediated diseases (pIMDs). pIMDs are a subset of AESIs that include autoimmune diseases and other inflammatory and/or neurologic disorders of interest which may or may not have an autoimmune etiology. AESIs that need to be recorded and reported as pIMDs for Stage 3 participants are listed in [Section 12](#).

However, the investigator will exercise their medical and scientific judgement in deciding whether other diseases have an autoimmune origin (that is pathophysiology involving systemic or organ-specific pathogenic autoantibodies) and should also be recorded as a pIMD.

When there is enough evidence to make any of the diagnoses mentioned in [Section 12](#), the AESI must be reported as a pIMD. Symptoms, signs or conditions which might (or might not) represent the above diagnoses, should be recorded and reported as AEs but not as pIMDs until the final or definitive diagnosis has been determined, and alternative diagnoses have been eliminated or shown to be less likely.

New Onset of Chronic Medical Conditions (NOCMCs) are defined as any new ICD diagnosis (per current International Statistical Classification of Diseases and Related Health Problems) that is applied to the subject during the course of the study, after receipt of the study agent, that is expected to continue for at least 3 months and requires continued health care intervention.

Medically Attended Adverse Events (MAAEs) are defined as a hospitalization < 24 hours, emergency room visit or an otherwise unscheduled visit to or from medical personnel for any reason; and considered related or possibly related to study product.

All AESIs, MAAEs, NOCMCs, are assessed, recorded, and followed as described above under AEs. The following need to be reported to DMID pharmacovigilance:

All AESIs, MAAEs or NOCMCs that meet SAE criteria (reported within 24 hours);
Any AESIs even if not SAE (reported within 24 hours);
MAAEs only when requested by the sponsor;
NOCMCs only when requested by the sponsor.

As indicated, these should be reported to DMID Pharmacovigilance Group at the following address:

DMID Pharmacovigilance Group
Clinical Research Operations and Management Support (CROMS)
[name]
[name]
SAE Hot Line: [name] (US) or [name] (outside US)
SAE [contact] (US) or [name] (outside US)
SAE Email Address: [contact]

8.3.10 Reporting of Pregnancy

Pregnancy is not an AE. Pregnancy outcomes will be reported on the appropriate DCF if a new pregnancy occurs within 3 months from last study vaccine dose. If pregnancy is associated with an SAE to the mother or fetus (e.g., miscarriage or preeclampsia), the SAE should be reported to PVG.

8.4 Unanticipated Problems

8.4.1 Definition of Unanticipated Problems (UPs)

The Department of Health and Human Services (DHHS) OHRP considers unanticipated problems involving risks to subjects or others to include, in general, any incident, experience, or outcome that meets all of the following criteria:

- Unexpected in terms of nature, severity, or frequency given (a) the research procedures that are described in the protocol-related documents, such as the IRB-approved research protocol and informed consent document; and (b) the characteristics of the subject population being studied;
- Related or possibly related to participation in the research (“possibly related” means there is a reasonable possibility that the incident, experience, or outcome may have been caused by the procedures involved in the research); and
- Suggests that the research places subjects or others at a greater risk of harm (including physical, psychological, economic, or social harm) than was previously known or recognized.

8.4.2 Unanticipated Problem Reporting

To satisfy the requirement for prompt reporting, UPs will be reported using the following timeline:

- UPs that are SAEs will be reported to the IRB, to the DMID Pharmacovigilance Group, and in the clinical database within 24 hours of the participating site PI or appropriate sub-investigator becoming aware of the event per the above-described SAE reporting process.
- UPs that are SAEs will be collected from Day 1 through the end of the study.
- Any other UP will be reported to the IRB and in the clinical database within 3 days of the participating site PI or appropriate sub-investigator becoming aware of the problem.

8.4.3 Reporting Unanticipated Problems to Subjects

Subjects will be informed of any UPs that occur as part of their participation in this trial.

9. STATISTICAL CONSIDERATIONS

9.1 Statistical Hypotheses

This is a phase 2, open-label, multi-site clinical trial that is not designed to test a specific hypothesis. Rather, it is intended to obtain preliminary estimates in adults of the safety and immunogenicity of additional booster doses of SARS-CoV-2 variant vaccines.

9.2 Sample Size Determination

9.2.1 Sample Size Calculation for the Safety Endpoint

Rare AEs are not demonstrable in a clinical study of this size; however, the probabilities of observing one or more AEs given various true event rates are presented in [Table 5](#). With the assumption that all enrolled subjects will likely complete immunizations and safety visits in this relatively short duration study, the following statistical considerations apply. With approximately 100 subjects in each arm there is a greater than 99.9% chance of observing at least one AE of probability 10%. With approximately 50 subjects in each of the strata subgroups (or arms), there is a 99.5% chance of observing at least one AE of probability 10%. With approximately 25 subjects in each of the strata subgroup combinations (assuming equal numbers and 100 per arm), there is a 92.8% chance of observing at least one AE of probability 10%. Finally, with approximately 15 subjects in the smallest of the strata subgroup combinations (assuming unequal numbers and 100 per arm or 50 per arm), there is a 79.4% chance of observing at least one AE of probability 10%. Therefore, if no AEs of a given type occur in a group (or strata), we can be relatively confident that they will occur in fewer than 10% of people if the vaccine is implemented.

Table 5: Probability of Observing one or more Adverse Event for Various Event Rates in one vaccine group (or strata).

N	“True” Event Rate	Probability of Observing \geq 1 events (%)	N	“True” Event Rate	Probability of Observing \geq 1 events (%)
100	0.1%	9.5	50	0.1%	4.9
	0.5%	39.4		0.5%	22.2
	1.0%	63.4		1.0%	39.5
	2.0%	86.7		2.0%	63.6
	3.0%	95.2		3.0%	78.2
	4.0%	98.3		4.0%	87
	5.0%	99.4		5.0%	92.3
	10.0%	>99.9		10.0%	99.5
	15.0%	>99.9		15.0%	>99.9
	20.0%	>99.9		20.0%	>99.9
	30.0%	>99.9		30.0%	>99.9

N	“True” Event Rate	Probability of Observing ≥ 1 events (%)	N	“True” Event Rate	Probability of Observing ≥ 1 events (%)
25	0.1%	2.5	15	0.1%	1.5
	0.5%	11.8		0.5%	7.2
	1.0%	22.2		1.0%	14
	2.0%	39.7		2.0%	26.1
	3.0%	53.3		3.0%	36.7
	4.0%	64.0		4.0%	45.8
	5.0%	72.3		5.0%	53.7
	10.0%	92.8		10.0%	79.4
	15.0%	98.3		15.0%	91.3
	20.0%	99.6		20.0%	96.5
	30.0%	>99.9		30.0%	99.5

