To evaluate humoral immune responses of candidate SARS-CoV-2 variant vaccines, alone or in combination.

Secondary

1. To evaluate the safety of candidate SARS-CoV-2 variant vaccines, as assessed by:
 - Local and systemic solicited Adverse Events for 7 days following each vaccine dose.
 - Unsolicited Adverse Events from Dose 1 to 28 days following each vaccine dose.
 - SAEs, MAAEs, AESIs, NOCMCs, and AEs leading to withdrawal from the study from Dose 1 to 12 months after last vaccine dose.

Exploratory:

1. To assess, in at least a subset of samples, the B cell immune response of candidate SARS-CoV-2 variant vaccines.
2. To assess, in at least a subset of samples, the SARS-CoV-2 spike protein-specific T cell responses of candidate SARS-CoV-2 variant vaccines.
3. To assess, in at least a subset of samples, the magnitude, phenotype, and percentage of innate immune cells with candidate SARS-CoV-2 variant vaccines.
4. To assess, in at least a subset of samples, the functional potential of SARS-CoV-2 specific antibodies to mediate Fc-effector functions across candidate SARS-CoV-2 variant vaccines.
5. To evaluate breakthrough SARS-CoV-2 infection by sequencing strains for variant spike lineage and assessing anti- nucleocapsid serology.

Study Design:

This is a Phase 2 randomized open label, non-placebo controlled, multi-site, multi-stage clinical trial in individuals, 18 years of age and older, who are in stable state of health, have received a complete authorized/approved vaccine series (primary series + a booster either with homologous or heterologous vaccine products) \geq 16 weeks prior to enrollment.

Subjects will be stratified by i) age (18-64 years and \geq 65 years of age) (however arms 16 and 17 or stage 4 will only enroll participants between the ages of 18-49 years) and ii) history of confirmed prior SARS-CoV-2 infection, and randomly assigned to receive one of several variant vaccines. Enrollment will target a goal of approximately 45% of each of the variant vaccine arms to be in

older adults (≥ 65 years of age) for stages 1, 2 and 3 and approximately 20% to have had confirmed COVID-19 for all 4 stages.

This is an adaptive design and may add arms of new vaccine platforms and/or variant lineage spike vaccines as needed. The study arms will be conducted in different stages (that could overlap) depending on public health needs and availability of study products (starting with the available mRNA vaccines).

Table 1: Study Arms

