	Arms	Vaccine Platform	Sample Size	Vaccine Candidate	Interval (weeks)*	Timing of First Dose	Timing of Second Dose
Stage 1	1	Moderna mRNA-1273	100	Prototype	≥ 16	D1	NA
	2		100	Beta + Omicron	≥ 16	D1	NA
	3		100	Beta + Omicron	≥ 16	D1	D57
	4		100	Delta + Omicron	≥ 16	D1	NA
	5		100	Omicron	≥ 16	D1	NA
	6		100	Omicron + Prototype	≥ 16	D1	NA
Stage 2	7	Pfizer/ BioNTech BNT162b2	50	Wildtype (Prototype)	≥ 16	D1	NA
	8		50	Beta + Omicron	≥ 16	D1	NA
	9		50	Omicron	≥ 16	D1	NA
	10		50	Beta	≥ 16	D1	NA
	11		50	Beta + Wildtype	≥ 16	D1	NA
	12		50	Omicron + Wildtype	≥ 16	D1	NA
Stage 3	13	Sanofi CoV2 preS dTM-AS03	50	Prototype	≥ 16	D1	NA
	14		50	Beta	≥ 16	D1	NA
	15		50	Beta+ Prototype	≥ 16	D1	NA
Stage 4	16^	Pfizer/ BioNTech BNT162b2 bivalent	100	Omicron BA.1 + Wildtype (Prototype)	≥ 16	D1	NA
	17^		100	Omicron BA.4/BA.5 + Wildtype (Prototype)	≥ 16	D1	NA

Two age strata:

- 18-64 years
- ≥ 65 years (~45% in ≥ 65 years).

^For arms 16 and 17 or stage 4, only participants between the ages of 18 to 49 years will be enrolled.

Two infection strata:

- Confirmed prior SARS-CoV-2 infection (~20%)
- No known history of prior infection.

*interval (in weeks) since last exposure to SARS-CoV-2 infection or vaccination

Duration of Study: Up to 4 years

Duration of participation per subject: Up to 2 years (approximately 12 months after last inoculation)

Criteria for Inclusion/Exclusion:

Inclusion Criteria:

Participants must meet all of the following criteria to be eligible to participate in this study:

1. Individuals \geq 18 years of age at the time of consent (18-49 years for stage 4).
2. Confirmed receipt of a complete primary and booster COVID-19 vaccine series, either homologous or heterologous, with an FDA authorized/approved vaccine at least 16 weeks prior to study vaccine dose 1.
3. Willing and able to comply with all scheduled visits, vaccination plan, laboratory tests and other study procedures.
4. Determined by medical history, targeted physical examination and clinical judgement of the investigator to be in stable state of health.

Note: Participants with pre-existing stable chronic medical conditions defined as condition not requiring significant change in therapy or hospitalization for worsening disease within 4 weeks from enrollment, can be included at the discretion of the investigator.

Exclusion Criteria:

Participants meeting any of the following criteria will be excluded from the study:

1. Confirmed SARS-CoV-2 infection $<$ 16 weeks prior to any study vaccine dose.

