9.2.2 Sample Size Calculation for the Immunogenicity Endpoints

The primary objective of this study is to evaluate the magnitude and durability of SARS-CoV-2 specific antibody titers in serum samples. This objective is descriptive in nature and will be accomplished by estimating 95% confidence intervals (CI) for the geometric mean titer (GMT) at each timepoint when samples are collected.

The precision with which the GMT can be estimated from observed data depends on the standard deviation (SD) of the measurements, on the logarithmic scale, and the sample size. [Table 6](#) displays two-sided 95% confidence intervals for the GMT for several values of the observed antibody titer. [Table 6](#) also shows results assuming up to 10% attrition.

Table 6: Two-sided 95% confidence intervals based on observing a particular average \log_e -antibody titer in subjects' vaccine groups and potential strata sizes

Observed average \log_e antibody titer	SD of \log_e antibody titer	95% confidence interval of GMT in vaccine groups and strata			
		N = 100	N = 50	N = 25	N = 15
$\log_e(5)$	0.5	(4.5, 5.5)	(4.3, 5.8)	(4.1, 6.1)	(3.8, 6.6)
$\log_e(20)$		(18.1, 22.1)	(17.4, 23.1)	(16.3, 24.6)	(15.2, 26.4)
$\log_e(50)$		(45.3, 55.2)	(43.4, 57.6)	(40.7, 61.5)	(37.9, 66)
$\log_e(100)$		(90.6, 110.4)	(86.8, 115.3)	(81.4, 122.9)	(75.8, 131.9)
$\log_e(250)$		(226.4, 276.1)	(216.9, 288.2)	(203.4, 307.3)	(189.5, 329.8)
$\log_e(500)$		(452.8, 552.1)	(433.8, 576.3)	(406.8, 614.6)	(379.1, 659.5)
$\log_e(1000)$		(905.6, 1104.3)	(867.5, 1152.7)	(813.5, 1229.2)	(758.1, 1319)
$\log_e(5)$	1.0	(4.1, 6.1)	(3.8, 6.6)	(3.3, 7.6)	(2.9, 8.7)

Observed average \log_e antibody titer	SD of \log_e antibody titer	95% confidence interval of GMT in vaccine groups and strata			
		N = 100	N = 50	N = 25	N = 15
\log_e (20)		(16.4, 24.4)	(15.1, 26.6)	(13.2, 30.2)	(11.5, 34.8)
\log_e (50)		(41, 61)	(37.6, 66.4)	(33.1, 75.6)	(28.7, 87)
\log_e (100)		(82, 121.9)	(75.3, 132.9)	(66.2, 151.1)	(57.5, 174)
\log_e (250)		(205, 304.9)	(188.2, 332.2)	(165.5, 377.8)	(143.7, 435)
\log_e (500)		(410, 609.7)	(376.3, 664.3)	(330.9, 755.5)	(287.4, 869.9)
\log_e (1000)		(820, 1219.5)	(752.6, 1328.7)	(661.8, 1511)	(574.8, 1739.8)

* Assumes approximately 10% attrition.

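### Section 9.2.1 gives every stratum about 50 subjects, but the confirmed-infection stratum is planned at about 20 per 100-subject arm and about 10 per 50-subject arm

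*Protocol*

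**What the plan says.** Protocol section 9.2.1 works down through four group sizes: 100, 50, 25 and 15. For the second it says: "approximately 50 subjects in each of the strata subgroups (or arms), there is a 99.5% chance of observing at least one AE", where the true event rate is taken as 10%. Stated assumptions of equal or unequal numbers appear only in the two later sentences, which deal with combinations of strata (25 and 15 subjects). The sentence on 50 subjects has no such qualification. The paragraph ends by concluding that, if an event type is not seen in a group or stratum, one can be fairly confident that its true rate is below 10%.

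Section 1.1 defines two stratification factors, age and history of confirmed prior infection. About 45% are to be aged 65 or older in stages 1 to 3, and "approximately 20% to have had confirmed COVID-19 for all 4 stages". Table 1 gives 100 subjects to each of arms 1–6 and 16–17, and 50 to each of arms 7–15. Its footnote adds: "For arms 16 and 17 or stage 4, only participants between the ages of 18 to 49 years will be enrolled".

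Table 6 in section 9.2.2 gives GMT confidence intervals for the same four sizes, described as "subjects' vaccine groups and potential strata sizes". Section 9.4.7 names age group and infection status as the possible subgroup factors.

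**The concern.** A stratum of about 50 in a 100-subject arm requires a roughly even split. Age comes close to that in stage 1. Infection does not: a 20% target gives strata of about 20 and 80. In stage 4 everyone is aged 18–49 and so falls in the younger age stratum. Infection is then the only factor that divides an arm, and neither of its strata is near 50. In the 50-subject arms the confirmed-infection stratum is about 10, which is smaller than any size in Table 5 or Table 6.

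The trial tests no hypothesis, so these detection probabilities and interval widths are the whole of its sample-size justification. A reader who takes section 9.2.1 literally would apply the 50-subject figures to previously infected participants within an arm. That reader would overrate both what an absence of events shows and how precisely a GMT is estimated in that group.

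**Working it through.** **Inputs**

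- True event rate: 10%, with 5% as a second row of Table 5 (section 9.2.1).
- Arm sizes: 100 in arms 1–6 and 16–17; 50 in arms 7–15 (Table 1).
- Confirmed-infection share: about 20%, all stages (section 1.1).
- Older-adult share: about 45%, stages 1–3 (section 1.1).
- Dropout: none, as section 9.2.1 assumes for safety.

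**Reproducing the plan's figures.** P(at least one event) = 1 − (1 − p)^n. At p = 0.10:

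- n = 100: 99.997% (stated as above 99.9%)
- n = 50: 1 − 0.9^50 = 99.5% (stated 99.5%)
- n = 25: 92.8% (stated 92.8%)
- n = 15: 79.4% (stated 79.4%)

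All four agree, so only the stratum size is in question.

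**Stratum sizes implied by the targets**

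- 100-subject arm, infection: 0.20 × 100 = 20 confirmed, 80 with no known history.
- 100-subject arm in stage 1, age: 45 and 55. These give 99.1% and 99.7%, so about 50 is a fair description.
- 50-subject arm, infection: 0.20 × 50 = 10 confirmed, 40 with no known history.
- 50-subject arm, age: 22–23 and 27–28, giving about 90% to 95%. No stratum on either factor reaches 50 in these arms.

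**Detection probability and zero-event bound.** The one-sided 95% upper bound on the rate after zero events is 1 − 0.05^(1/n).

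| n | Where it arises | P(≥1), rate 10% | P(≥1), rate 5% | Upper bound, 0 events |
|---|---|---|---|---|
| 50 | as stated | 99.5% | 92.3% | 5.8% |
| 20 | confirmed infection, 100-subject arm | 87.8% | 64.2% | 13.9% |
| 10 | confirmed infection, 50-subject arm | 65.1% | 40.1% | 25.9% |

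For the upper bound to fall below 10%, 0.9^n must be below 0.05, so n must exceed ln 0.05 / ln 0.9 = 28.4, that is, at least 29 subjects. Neither 20 nor 10 reaches this.

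**GMT precision.** The interval is GMT × exp(± t(0.975, n−1) × SD / √n). For a GMT of 1000 and a log SD of 1.0:

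- n = 50: 752.6 to 1328.7, which matches Table 6
- n = 20: 626.2 to 1596.8
- n = 10: 489.0 to 2044.9

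**Sensitivity.** Section 4.1 expects about 40% with any prior infection once undiagnosed cases are counted. A group of 40 in a 100-subject arm gives 98.5% at a 10% rate, 87.1% at a 5% rate and an upper bound of 7.2%.

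**The case against.** Nothing is miscalculated. The sentence is conditional on 50 subjects, and its mention of arms makes it correct for arms 7–15 taken whole. In a stage 1 arm, three of the four single-factor strata are either near 50 or well above it: the two age strata, and the no-known-infection stratum at about 80 (99.98%). A stratum of 20 lies between the tabulated sizes of 25 and 15. Results will be reported with confidence intervals based on the numbers actually observed (sections 9.4.2 and 9.4.4), so nobody need read them off planning tables. The subgroup in section 9.4.7 might be defined in the SAP to include undiagnosed infection, which would bring the size to about 40. The 20% is also only a target, and section 4.1 lets the team slow enrolment of particular groups.

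Much of this limits the consequence, and two parts limit the scope. The shortfall in 100-subject arms is in one level of the infection factor, and in those arms a reader could interpolate between tabulated sizes. The conflict itself remains. The text assigns about 50 to each stratum without qualification, while the protocol defines the stratum by confirmed infection and targets about 20%. The tabulated sizes of 25 and 15 are assigned to combinations of strata, not to this stratum, and no tabulated size covers the 10 expected in arms 7–15. The 40% figure describes a different group from the one used for stratification.

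**Conclusion.** The point holds. For the confirmed-infection stratum the stated 99.5% should be about 87.8% in the 100-subject arms and about 65.1% in the 50-subject arms. The below-10% inference after zero events fails at the 95% level in both cases. This rests on the 20% target being met, on no dropout, and on the stratum being confirmed infection as section 1.1 defines it. If the analysis subgroup also counted undiagnosed infection at the anticipated 40%, the gap in a 100-subject arm would shrink to about one percentage point (98.5%).

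This should be corrected, but it is not critical. The trial is descriptive, and neither the arm sizes nor the halting rules are derived from this probability.

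**What to change.** In section 9.2.1, restrict the statement about 50 subjects and 99.5% to the age strata of the stage 1 arms and to the 50-subject arms as a whole. Then state the confirmed-infection stratum separately: about 20 per 100-subject arm (87.8% chance of at least one event of probability 10%) and about 10 per 50-subject arm (65.1%). Note that stage 4 is divided by infection status only, into about 20 and 80. Limit the closing below-10% inference to groups large enough to support it, or give the zero-event upper bound for each size. Add N = 20 and N = 10 to Tables 5 and 6.

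The cost is text and table edits in sections 9.2.1 and 9.2.2, and less favourable published figures for previously infected participants. Enrolment, arm sizes and conduct are unaffected.
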